7.6.5 Clinical Laboratory Evaluations

Summaries of laboratory test results and the corresponding change from baseline by treatment and nominal visit will be provided for those laboratory tests required at each study visit as given in Table 5.3.7-1 of the protocol.

The criteria used for classifying laboratory test results as markedly abnormal will be listed. These criteria are provided in an appendix to this SAP.

Laboratory results for subjects with any marked laboratory abnormality (scheduled and unscheduled) will be listed. This listing will include all observations for the specific laboratory test and subject, not only the marked laboratory abnormalities. The frequency of subjects with any marked laboratory abnormality will be presented by treatment and study time period (1A, 2A, 2B), and for study part 2.

In addition to the analysis of standard laboratory results, separate analyses will focus specifically on renal parameters. Renal biomarkers, including Cystatin-C, NGAL, and KIM-1 will be summarized according to the number and percentage of subjects in each treatment group with levels exceeding the upper limit of normal (ULN) at each study visit where labs are collected per protocol. Additionally, estimated Glomerular Filtration Rate (eGFR) using the Modification of Diet in Renal Disease formula (MDRD) will be summarized at each visit by the mean, standard deviation, range, and median.

Urinalysis results will also be summarized in the same manner as the laboratory test results.

7.6.6 *Electrocardiograms*

Summaries of ECG results and the corresponding change from baseline by treatment will be provided for the screening, Day 28, and end of treatment visits. The normality/abnormality of the ECG tracing, as determined by the investigator, will be summarized using frequency tables on the number of subjects who have a normal/abnormal ECG tracing at Day 28 and at Day 90 (Part 2 only). A listing of subjects with Investigator identified ECG abnormalities will also be provided.

7.6.7 *Vital Signs*

Vital sign measurements (systolic BP, diastolic BP, heart rate, respiratory rate and body temperature) and their respective changes from baseline will be summarized by nominal visit and treatment group.

The following criteria will be used to determine vital sign results that are out a range, where changes from baseline are based on matched postural positions:

Table 7.6.7-1: Out of Range Vital Signs Criteria

Vital Sign Measurement	Criteria
Heart Rate(bpm)	Value > 100 and change from baseline > 30, or Value < 55 and change from baseline < -15
Systolic BP(mmHg)	Value > 140 and change from baseline > 20, or Value < 90 and change from baseline < -20
Diastolic BP(mmHg)	Value > 90 and change from baseline > 10, or Value < 55 and change from baseline < -10

Subjects with vital signs out of range will also be listed.

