1.5 Overall Risk/Benefit Assessment

The current study is a Phase 2 study of BMS-986141 in patients with ischemic stroke or TIA who are also receiving ASA. Prior to this study BMS-986141 has only been dosed in healthy subjects.

Preclinical studies in non-human primates suggest that BMS 986141 may be more effective at preventing the growth of an arterial thrombus than treatment with ASA alone. Furthermore, substantial antithrombotic efficacy has been observed at doses which increase provoked bleeding to an extent that is comparable to or less than that of ASA. Thus BMS-986141 may have the potential to provide an improved benefit-risk profile compared to existing therapies for the prevention and/or treatment of atherothrombotic diseases such as stroke.

The study and dosing scheme described herein has been designed to minimize risks to study subjects and is based on the previous clinical experience in healthy subjects and preclinical toxicity studies as described in the Investigator Brochure. There were no adverse findings in 28-day preclinical toxicology studies. In 3-month studies, the major preclinical findings of note were microscopic changes in kidneys of some of the monkeys that received the highest dose of BMS-986141, 75 mg/kg/day. These changes have been characterized as moderate degeneration and regeneration of tubular epithelium, and the effect was not observed one month after cessation of dosing. Monitoring of kidney function, urinalysis, and exploratory renal biomarkers will occur throughout the treatment period to facilitate early identification of renal abnormalities in subjects in the study.

The doses selected for this study are projected to span the anticipated pharmacologically active dose range and are considered within the safety margin indicated by the preclinical toxicology and the clinical experience in healthy volunteers. Of note, co-administration of moderate inhibitors of CYP3A4 (eg, diltiazem, verapamil) have the potential of increasing exposures of BMS-986141 beyond those observed with ASA co-administration. However, it is not anticipated that exposures will exceed those observed in Phase 1 study (CV006003).

While bleeding was not observed to any significant degree either pre-clinically or in healthy volunteers, there is a potential risk of bleeding with any antithrombotic agent. There will therefore be close monitoring of subjects for bleeding and oversight of the study by an independent Data Monitoring Committee (DMC).

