3.3.2 Exclusion Criteria

1. Target Disease Exceptions

- a) Any history of atrial fibrillation (AF) other than transient AF related to cardiac surgery
- b) Severe left ventricular systolic dysfunction, left ventricular thrombus, or other high-risk cardioembolic source deemed the likely cause of brain ischemia
- c) TIA symptoms limited to isolated numbness, isolated visual changes, or isolated dizziness/vertigo
- d) Carotid or vertebral stenosis for which there is a plan for revascularization therapy
- e) Any condition requiring ongoing treatment with an anticoagulant after discharge. For prophylactic measures to prevent deep vein thrombosis (DVT), pneumatic pressure devices are preferred

2. Medical History and Concurrent Diseases

- a) Subjects with known bleeding diathesis or coagulation disorder (eg, thrombotic thrombocytopenic purpura)
- b) History of previous non-traumatic or traumatic intracranial hemorrhage at any time
- c) Acute gastrointestinal ulcer or history of gastrointestinal (GI) bleed which required medical treatment within the past 3 months

- d) Planned or anticipated invasive surgery or procedure during study duration
- e) Persistent, uncontrolled hypertension (systolic BP > 180 mm Hg, or diastolic BP > 100 mm Hg) that does not respond to acute treatment
- f) Moderate or severe hepatic impairment, defined as Child-Pugh Class B or C; (see [Appendix 5](#))
- g) Moderate to severe renal impairment, defined as estimated glomerular filtration rate (eGFR) < 45 mL/min; (see [Section 5.3.7.1](#))
- h) Any other reason, in the opinion of the investigator that the subject may be at undue risk from study participation
- i) Qualifying ischemic event induced by angiography or surgery
- j) Any gastrointestinal surgery that could impact upon the absorption of study drug
- k) Inability to tolerate oral medication or swallow tablets whole
- l) Inability to undergo venipuncture and/or tolerate venous access
- m) Subjects in whom MRI procedures cannot be performed. [Section 3.4.3](#) provides a list of some common conditions that may preclude the subjects from having MRI. However, this should not be used as a substitute for local clinical standards of care. The ultimate decision to perform any of these procedures in an individual subject in this study rests with the site radiologist, the investigator and the standard set by the local ethics committee/institutional review board

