8.4.5 Biomarker Analyses

Summary statistics will be tabulated for each available biomarker endpoint, including corresponding changes from baseline and/or percentage changes from baseline (where applicable) by treatment, and time point. Plots of means and standard errors over time and change from baseline (and/or percent change from baseline) for each available biomarker versus time may be provided. Relationships between exploratory biomarkers and BMS-986141 plasma concentrations may be explored. In addition, relationships between polymorphism in genes related to PAR4 activity (and/or disposition of BMS-986141) and exploratory biomarkers, PK parameters, or efficacy endpoints may be explored. Exploratory biomarker results may be reported separately.

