4.5 Additional Safety Endpoints

Additional safety endpoints include the incidence of adjudicated major bleeding events, all bleeding events, intracranial hemorrhage events, as well as the incidence of AEs and markedly abnormal standard clinical laboratory test results. As well, vital signs, ECG results, physical exam findings, and certain renal parameters and biomarkers, including estimated glomerular filtration rate (eGFR), Cystatin-C, NGAL, and KIM-1 may be considered as additional safety endpoints.

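### SAP 7.6.5 commits the safety section only to a visit-wise count above ULN for Cystatin-C, NGAL and KIM-1; a baseline-adjusted continuous summary should be added and the count split by pre-dose status.

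*SAP*

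**What the plan says.** SAP 7.6.5 gives the three renal biomarkers one summary: they "will be summarized according to the number and percentage of subjects in each treatment group with levels exceeding the upper limit of normal (ULN"). This is repeated for every visit that has protocol laboratory sampling. The rest of that section does not extend it:

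- "Summaries of laboratory test results and the corresponding change from baseline by treatment and nominal visit will be provided", but only for the tests in protocol Table 5.3.7-1. That table includes creatinine and BUN and omits all three biomarkers.
- eGFR stays on its continuous scale and "will be summarized at each visit by the mean, standard deviation, range, and median".
- The marked-abnormality criteria in SAP Appendices 1 and 2 do not list the three biomarkers.

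SAP 7.1.1 adds that abnormal renal biomarker results are tabulated by study time period (1A, 2A, 2B) and for Part 2.

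On purpose and status, protocol 1.5 says, as part of its renal monitoring, that "exploratory renal biomarkers will occur throughout the treatment period to facilitate early identification of renal abnormalities in subjects in the study". SAP 4.5 says that "certain renal parameters and biomarkers, including estimated glomerular filtration rate (eGFR), Cystatin-C, NGAL, and KIM-1 may be considered as additional safety endpoints".

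Elsewhere, protocol 8.4.5 plans summary statistics for each available biomarker by treatment and time point, including absolute or percentage change from baseline, and adds: "Exploratory biomarker results may be reported separately". SAP section 9 repeats that possibility. The Amendment 06 list of changes (item 34, on protocol 8.3.3) records that change from baseline on renal biomarkers was added as an exploratory endpoint. Protocol 8.3.3 and SAP 4.3 and 7.8 are redacted.

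**The concern.** Amendment 06 gives a kidney tubular finding in monkeys as the reason for lowering the top dose, delaying the 8 mg arm and adding renal biomarkers. The safety section should therefore be able to show a small dose-related shift in these markers. A count above ULN has two weaknesses for that purpose.

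1. It drops the scale. A rise that stays within the normal range does not appear in the table.
2. It does not link a subject's later value to the pre-dose value, so a subject above ULN before the first dose can be counted again at every later visit. Such subjects may be enrolled. The renal exclusion is "Moderate to severe renal impairment, defined as estimated glomerular filtration rate (eGFR) < 45 mL/min", and entry is within 48 hours of a stroke or TIA. The documents do not say how many there will be.

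Of the renal measures in 7.6.5, only these three have neither a continuous nor a baseline-referenced summary. Elsewhere the SAP does use the pre-dose value: for leukocytes, electrolytes, LDH, uric acid and urinalysis in Appendix 1, and for out-of-range vital signs in Table 7.6.7-1. At stake is whether a reader of the safety tables sees a modest shift that the samples could show.

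**Working it through.** The documents state no power, SD, effect size or ULN rate for these markers, so there is no planned figure to reproduce. Everything below about the markers is an assumption.

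**Inputs**
- 270 subjects per arm: 8 mg and concurrent placebo after the DMC review (SAP Table 5-1).
- Assumed: marker normal on the log scale; every treated subject shifts by d SD; proportion p of placebo subjects above ULN is 5–30%; correlation rho with the pre-dose value is 0.5–0.7; two-sided 0.05.

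**Information kept by the count.** Relative to comparing means, it is phi(z_p)² / [p(1 − p)]; relative to a baseline-adjusted comparison, multiply by (1 − rho²). For p = 0.10: 0.1755² / 0.09 = 0.34.

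| p above ULN | vs means | vs adjusted, rho 0.5 | vs adjusted, rho 0.7 |
|---|---|---|---|
| 5% | 0.22 | 0.17 | 0.11 |
| 10% | 0.34 | 0.26 | 0.17 |
| 20% | 0.49 | 0.37 | 0.25 |
| 30% | 0.58 | 0.43 | 0.29 |

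**Power, uniform shift.** For the count, p1 = 1 − Phi(z_p − d) with unpooled SE. Example, p = 0.20 and d = 0.25: p1 = 0.277, SE = 0.0365, z = 0.0771/0.0365 = 2.11, power 56%. For means, z = d / sqrt(2/270) = 0.25/0.0861 = 2.91, power 83%. With baseline adjustment the SE is multiplied by sqrt(1 − rho²).

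| Shift | Count above ULN (p 5–30%) | Means | Adjusted (rho 0.5–0.7) |
|---|---|---|---|
| 0.25 SD | 32–62% | 83% | 92–98% |
| 0.15 SD | 14–27% | 41% | 52–69% |

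Using all 348 placebo subjects against 270 gives the same picture for 0.25 SD: 49%, 61% and 67% for the count at p = 10%, 20% and 30%, 87% for means and 99% adjusted (rho 0.7).

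**Pre-existing elevations.** With no drug effect, the share of subjects above ULN at a later visit who were already above it pre-dose is P(both above)/p under a bivariate normal. It runs from 24% (p = 5%, rho 0.5) to 64% (p = 30%, rho 0.7).

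**Would a treatment-emergent count alone be better?** Take p = 20%, d = 0.25, and only subjects at or below ULN pre-dose (270 × 0.8 = 216 per arm). New elevations are 14.1% vs 21.0% (rho 0.5) or 10.9% vs 17.5% (rho 0.7). Power is 47–50%, below the 56% of the plain count.

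**A different shape of effect.** Suppose 5% of treated subjects rise by 3 SD and the rest do not move. At p = 5%, p1 = 0.95 × 0.05 + 0.05 × Phi(3 − 1.645) = 0.093. Power is 50% for the count, 35% for means and 43–54% adjusted. At p = 2.5% the count reaches 64%; at p = 20–30% it falls to 20–14%. The power of the means and adjusted comparisons does not depend on p.

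**The case against.** A reader might infer that most of the information on a kidney signal is lost to the trial. The documents do not support that. Protocol 8.4.5 plans change from baseline for each available biomarker, the list of changes names renal biomarkers specifically, and the SAP section that would carry this is redacted and cannot be called empty. Separate reporting is a possibility, not a decision. Even within 7.6.5, against unadjusted means the count keeps more than half the information at 30% above ULN (0.58).

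A reader might also infer that pre-existing elevations make the table misleading between arms. Randomization balances them between concurrent arms, and the by-period tables keep those comparisons available. On a plain reading the per-visit table also includes Day 1, so the starting rate per arm would be visible. What is missing is the link within each subject.

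The SAP is not out of line with itself either: in Appendix 1 the liver and kidney tests, creatinine and BUN among them, use plain ULN multiples with no pre-dose limb. Creatinine and BUN do, however, also get change from baseline, and urinalysis is summarized as the laboratory tests are. The table is for the final report; the data for the DMC's 8 mg decision are set in its charter.

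Finally, the power figures test a hypothesis the SAP does not plan to test, and they assume a uniform shift. Protocol 1.5 reports the tubular change in some of the high-dose monkeys, and for an effect confined to a few subjects the count can do better than means.

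All of this stands, and it limits the point to what 7.6.5 itself commits. It also argues for keeping the count. It does not remove the gap: if the biomarker results are reported elsewhere, the visible text leaves the safety section with the count alone.

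**Conclusion.** The point holds for the safety summary in SAP 7.6.5, and no further. For a modest overall shift, the committed count is clearly weaker than a baseline-adjusted comparison of values: it keeps about 11–43% of the information over the assumed range, and for a 0.25 SD shift has 32–62% power against 92–98%. It also mixes old and new elevations, which dilutes contrasts between concurrent arms without biasing them.

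These figures rest on assumed log-normal markers, ULN rates of 5–30%, baseline correlations of 0.5–0.7 and a uniform shift; none comes from the documents. The ordering can reverse when only a few subjects rise sharply, so neither summary replaces the other. The change is worth making because it is cheap and the markers were added for renal safety. The primary analysis and sample size are unaffected.

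**What to change.** In SAP 7.6.5, for Cystatin-C, NGAL and KIM-1:

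1. Add, by arm and visit, the log ratio to the pre-dose value. Give the geometric mean ratio of each BMS-986141 arm to placebo with its 95% CI, from an ANCOVA on the log value with log baseline and study time period (1A, 2A, 2B) as covariates. At Day 56 and Day 90, which only Part 2 has, the periods reduce to 2A and 2B.
2. Label these estimates descriptive and place them in the safety section of the study report. If SAP 7.8 already provides them, a cross-reference and that placement are enough.
3. Keep the count above ULN. Beside it, show the counts split by pre-dose status (at or below ULN, above ULN). Do not replace the plain count with a treatment-emergent count alone.

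The cost is SAP wording and a few extra tables. No new samples should be needed: protocol Table 5.6.1-1 shows pre-dose Day 1 collection in both biomarker columns whose headings are redacted. The downside is that several estimates per visit will occasionally show a chance difference, hence the descriptive label.

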3.5 Discontinuation of Subjects following any Treatment with Study Drug

During treatment period circumstances may arise which require temporary or permanent discontinuation of investigational product. For guidance related to the temporary discontinuation please refer to [Section 3.4.1](#).

Subjects MUST discontinue investigational product (and non-investigational product at the discretion of the investigator) for any of the following reasons:

- Subject's request to stop study treatment
- Any clinical adverse event (AE), laboratory abnormality or intercurrent illness which, in the opinion of the investigator, indicates that continued participation in the study is not in the best interest of the subject
- Any clinical condition requiring treatment with a prohibited medication for more than 14 days
- Termination of the study by Bristol-Myers Squibb (BMS)
- Loss of ability to freely provide consent through imprisonment or involuntarily incarceration for treatment of either a psychiatric or physical (eg, infectious disease) illness
- Severe non-compliance to protocol, as judged by the investigator and/or Sponsor (BMS)
- Incorrect enrollment (ie, the subject does not meet the required inclusion/exclusion criteria) for the study, as determined after consultation with the sponsor
- Pregnancy
- Moderate or severe renal impairment defined as eGFR < 45 mL/min (see [section 5.3.7.1](#)) for more than 7 days.
- Subjects with an ALT and/or AST > 3× ULN will be scheduled for a follow up visit within 3 days following the receipt of the result. Subjects should be discontinued from study if the initial and repeat laboratory tests meet any of the following criteria:
 - ◆ ALT and/or AST are > 3× ULN and total bilirubin (TB) > 2× ULN

- ◆ ALT and/or AST are $> 5 \times$ ULN for ≥ 14 consecutive days, at any time after initial confirmatory results
- ◆ ALT and/or AST are $\geq 10 \times$ ULN
- Subjects requiring treatment with strong CYP3A4 inhibitors or strong CYP3A4 inducers
- Subjects treated with any intravenous or intra-arterial thrombolysis or with mechanical thrombectomy

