5.3.7.1 Renal Impairment

The exclusion and discontinuation criteria for severe renal impairment should be evaluated based on eGFR calculated by the local laboratory. In the event that eGFR is not reported by the local laboratory, it should be calculated by the Modification of Diet in Renal Disease (MDRD) Study Equation.

$$\text{eGFR} = 186 * \text{serum creatinine mg/dL}^{-1.154} * \text{Age}^{-0.203} [*0.742 \text{ if female}] [*1.212 \text{ if African American}]$$
^{6,7}

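### No planned table counts, by arm, the subjects whose eGFR falls below the protocol's 45 mL/min threshold or declines substantially from baseline

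*SAP*

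**What the plan says.** Kidney injury is the organ toxicity that the protocol singles out. Protocol 1.5 reports "microscopic changes in kidneys of some of the monkeys that received the highest dose of BMS-986141" in the 3-month studies, and says that monitoring of kidney function, urinalysis and "exploratory renal biomarkers will occur throughout the treatment period to facilitate early identification of renal abnormalities". The Amendment 06 rationale gives this finding as the reason for its safety changes, including the lower and later top dose.

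The protocol uses one eGFR value twice. Section 3.3.2 excludes "Moderate to severe renal impairment, defined as estimated glomerular filtration rate (eGFR) < 45 mL/min". Section 3.5 requires discontinuation of study drug for "Moderate or severe renal impairment defined as eGFR < 45 mL/min", provided that it lasts more than 7 days. Under section 5.3.7.1 both criteria "should be evaluated based on eGFR calculated by the local laboratory", with the MDRD equation as the fallback.

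SAP 4.5 lists eGFR among the possible additional safety endpoints. SAP 7.6.5 then provides:

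- **eGFR (MDRD):** it "will be summarized at each visit by the mean, standard deviation, range, and median".
- **Cystatin-C, NGAL and KIM-1:** number and percentage of subjects per arm "with levels exceeding the upper limit of normal (ULN) at each study visit where labs are collected per protocol".
- **Marked abnormalities:** "The frequency of subjects with any marked laboratory abnormality will be presented by treatment and study time period". The criteria are in Appendices 1 and 2. Creatinine is flagged above 1.5 x ULN and BUN above 2 x ULN, neither with a pre-dose limb. eGFR has no row.
- **Laboratory tests in protocol Table 5.3.7-1:** values and changes from baseline by treatment and visit. This covers creatinine and BUN; eGFR is not in that table.

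**The concern.** The four eGFR statistics describe a distribution. None says how many subjects in an arm fell below 45, or how many lost a large fraction of their own baseline. Eligible subjects enter at or above 45 by the local value, so a later value below 45 would usually be a new event, and it is the event that the protocol itself acts on.

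The creatinine flag would have to fill the gap, but it is tied to the laboratory's upper limit and not to the subject's starting value. Hemoglobin, hematocrit, erythrocytes, LDH and uric acid all have a pre-dose comparison in the same appendices; creatinine does not.

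At stake is the comparison of doses on the named organ risk. If harm took the form of large falls in a minority of subjects, the eGFR and creatinine tables would show it poorly. That pattern is an inference: the protocol reports microscopic changes in some top-dose animals and gives no creatinine or GFR data for them.

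**Working it through.** The plan states no figure to reproduce. The check has three parts.

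**1. Where does the creatinine flag sit relative to eGFR 45?**

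Inputs: the MDRD equation in protocol 5.3.7.1, eGFR = 186 x Cr^-1.154 x Age^-0.203 (x 0.742 if female; x 1.212 if African American), and the flag at 1.5 x ULN from the SAP appendices. The ULN is not in the documents. I assume 1.2-1.3 mg/dL for men and 1.0-1.1 mg/dL for women.

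At age 65 without the 1.212 factor, the constant before the creatinine term is 186 x 65^-0.203 = 79.7 for men and 79.7 x 0.742 = 59.1 for women.

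- Creatinine at eGFR 45: men (79.7/45)^(1/1.154) = 1.64 mg/dL; women (59.1/45)^(1/1.154) = 1.27 mg/dL.

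| Age 65 | Assumed ULN | Flag starts above (mg/dL) | eGFR at the flag | Same, x 1.212 |
|---|---|---|---|---|
| Men | 1.2 | 1.80 | 40.4 | 49.0 |
| Men | 1.3 | 1.95 | 36.9 | 44.7 |
| Women | 1.0 | 1.50 | 37.0 | 44.9 |
| Women | 1.1 | 1.65 | 33.2 | 40.2 |

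Without the factor, every row crosses 45 before the flag. With it, the answer depends on the ULN: a man with ULN 1.2 is flagged before reaching 45, and two of the other three rows sit almost exactly on it. For the flag to coincide with eGFR 45 without the factor, the ULN would have to be 1.64/1.5 = 1.09 (men) or 1.27/1.5 = 0.84 (women).

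Two examples:

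- A 65-year-old woman falling from eGFR 80 (creatinine 0.77) to 44 (1.29) loses (80 - 44)/80 = 45% and crosses 45. Her creatinine is not flagged at either assumed ULN.
- A 70-year-old man going from 0.8 to 1.2 mg/dL, within the assumed normal range, goes from eGFR 101.6 to 63.6, a 37% loss, also unflagged.

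**2. Could the visit statistics stand in for a count?**

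The range shows whether anyone is below 45, not how many. If 1% of an arm is truly below 45, the chance of at least one such subject is 1 - 0.99^348 = 97% for placebo and 1 - 0.99^270 = 93% for 8 mg (planned sizes, SAP Table 5-1). The minimum would be below 45 in nearly every arm.

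For the mean, suppose that an extra 5% of 8 mg subjects each lose 30 mL/min. The arm mean moves by 0.05 x 30 = 1.5 mL/min. With an assumed eGFR SD of 15 to 25, the standard error of the difference is SD x sqrt(1/348 + 1/270) = 1.22 to 2.03. The shift is about the size of its error. If those subjects all ended below 45, and 2% of each arm did so anyway, a count would show about 7 of 348 against 19 of 270. The scenario is illustrative only.

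**3. Would the discontinuation rule bring every crossing into another table?**

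In Part 1 (protocol Table 5.1-2), chemistry after the Day 1 pre-dose sample is scheduled only at discharge and Day 28; the Day 10 contact is by telephone. Section 4.5 ends Part 1 dosing on Day 28. The visit window is 3 days either side, so the earliest in-window Day 28 visit is Day 25, leaving at most 3 further days of dosing. A crossing first seen there cannot last more than 7 days on drug. In Part 2 the same holds for a crossing first seen at the end-of-treatment visit.

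**The case against.** The strongest reply is that the plan covers the kidney far better than the eGFR line suggests, and much of this stands.

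- Cystatin-C, NGAL and KIM-1 are counted by arm. KIM-1 and NGAL may show tubular injury without any fall in eGFR.
- The urine protein, blood, RBC and WBC criteria in the appendices do depend on the pre-dose value.
- Creatinine and BUN changes from baseline are summarised by treatment and visit.
- A crossing that lasts more than 7 days on drug requires discontinuation. Protocol 6.3 sends laboratory abnormalities that force discontinuation or interruption to the adverse-event form, and SAP 7.3.1 and 7.6.4 tabulate discontinuations by arm and period. Such subjects are counted, though not under an eGFR label.

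A reader might therefore go too far by inferring that a renal signal would appear only as an extreme value in a range, that the woman in the example is in no abnormality count, or that the dose comparison must be falsely reassuring. The documents support none of these: she could be counted for a biomarker or a urine abnormality, and a signal could show there. Nor do subjects who meet the full discontinuation criterion go uncounted; a single value below 45 does not meet it.

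The reply does not close the gap. None of these outputs counts transient crossings, crossings first seen at end of treatment, or large losses within range. Other adverse-event reporting depends largely on the investigator's judgement of significance, and no renal reason for discontinuation is specified. The biomarker counts are against ULN without regard to the subject's own baseline. The schedule in protocol Table 5.6.1-1 appears to include a pre-dose sample (column headings are blacked out), so baseline prevalence by arm may be visible, but not who changed.

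SAP 8.4 mentions shift analyses only within a windowing rule, and SAP 9 defers table detail to a Data Presentation Plan that is not among the documents. A count may exist there or in the sponsor's safety-analysis procedure; the SAP does not prespecify it.

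**Conclusion.** The point holds as an omission in prespecified safety reporting: the SAP has no by-arm count of eGFR below 45 or of substantial decline from baseline, and the creatinine criterion does not reliably substitute. At age 65 without the race factor, the flag lags the threshold by roughly 5 to 8 mL/min in men and 8 to 12 in women (45 minus the eGFR at the flag). Those sizes rest on the assumed ULNs; with the 1.212 factor some subjects are flagged before 45. The absence of a count does not depend on any ULN.

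A simple count below 45 would not reproduce the protocol's criterion, which uses the local-laboratory value and requires more than 7 days; the SAP uses MDRD and on-study chemistry is central. It would still be a useful descriptive measure if labelled as such. The trial's validity is not in question. The correction is worth making because the missing count concerns the organ risk for which the protocol added its renal monitoring.

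**What to change.** In SAP 7.6.5 add one descriptive table, by treatment and by study period (1A, 2A, 2B, and Part 2 overall), giving:

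- n (%) of subjects with a new post-baseline eGFR below 45 mL/min, among those at or above 45 at baseline. Restricting to new crossings matters because entry uses local eGFR, so a central Day 1 value may already be below 45.
- n (%) in one prespecified set of percent-decline-from-baseline eGFR categories, for example at least 30%. The documents give no cut-off, so the sponsor should choose and justify it. A separate rule of creatinine at least 1.5 x baseline would add little: under MDRD it is a fall of 1 - 1.5^-1.154 = 37%, already inside a 30% category.

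State which eGFR is used (central-laboratory MDRD), noting that the protocol rule uses the local value. Show Cystatin-C, NGAL and KIM-1 exceedances by baseline status, so that new elevations are separated from existing ones.

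The cost is SAP wording and one extra table from data already collected. Some transient changes unrelated to the drug will be counted in every arm. No clinical threshold or discontinuation rule changes.
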